- Ribavirin (RBV): in tablet form at the dose of 1000-1200 mg per day, weight based twice daily by mouth for 24 weeks
 - For subjects weighing < 75 kg at Day 1, the total dose is 1000 mg/day. Subjects should take 400 mg (2 x 200 mg tablets) in the morning with a meal, and 600 mg (3 x 200 mg tablets) in the evening with a meal
 - For subjects weighing ≥ 75 kg at Day 1, the total dose is 1200 mg/day. Subjects should take 600 mg (3 x 200 mg tablets) in the morning and in the evening with a meal

Study Phase: 3

Research Hypothesis:

Combination therapy with DCV and SOF plus RBV for 24 weeks is safe and demonstrates an SVR12 rate greater than the threshold SVR rate in chronically infected subjects with HCV GT-3 and cirrhosis.

Objectives:

Primary Objective

- To demonstrate the SVR12 rate, defined as HCV RNA < LLOQ target detected (TD) or target not detected (TND) at follow-up Week 12 in subjects treated with 24 weeks of DCV+SOF+RBV therapy is greater than the historical threshold SVR rate

Key Secondary Objective

- To assess the impact of baseline NS5A resistance-associated polymorphisms on the SVR12 rate

Secondary Objectives

- To assess safety, as measured by the frequency of deaths, serious adverse events (SAEs), discontinuation due to adverse events (AEs), Grade 3/4 AEs and Grade 3/4 laboratory abnormalities;
- To assess antiviral activity, as measured by:
 - The proportion of subjects who achieve HCV RNA < LLOQ, TD or TND at each of the following Weeks: 1, 2, 4, 8, 12, 16, 20, 24, and EOT; post-treatment Week 4 and 24
 - The proportion of subjects who achieve HCV RNA < LLOQ, TND at each of the following Weeks: 1, 2, 4, 8, 12, 16, 20, 24, and EOT

Study Design:

AI444379 is an open-label trial evaluating the combination therapy of DCV+ SOF with RBV for 24 weeks in subjects infected with HCV GT-3 with compensated cirrhosis. The study will include approximately 75 subjects.

[figure not shown]
Subjects will receive the combination of DCV 60 mg QD (unless concomitant HIV regimen dictates otherwise) + SOF 400 mg QD + RBV (weight based 1000 mg-1200 mg daily) for 24 weeks. HCV RNA will be available for review by the clinical site personnel. After treatment is completed subjects will be followed for 24 weeks. Subjects who discontinue early should be followed for 24 weeks post-treatment.

The primary analysis is SVR12 and the final analysis is SVR24.

Duration of study:

The screening/enrollment period is anticipated to be approximately 8 weeks from FPFV to LPFV. Study duration will be 52 weeks (4 week screening period, 24 weeks of therapy, and 24 weeks of follow-up).

Study Design Subjects with GT-3 Infection with Cirrhosis

Study Population:

The key subject population will be subjects chronically infected with HCV GT-3 with compensated cirrhosis. Subjects with cirrhosis who are mono-infected with HCV genotype 3 or coinfecte

Study Drug: includes both Investigational [Medicinal] Products (IP/IMP) and Non-investigational [Medicinal] Products (Non-IP/Non-IMP) as listed:

Study Drug for AI444379		
Medication	Potency	IP/Non-IP
Daclatasvir, BMS-790052	60 mg	IP
Daclatasvir, BMS-790052	30 mg	IP
Sofosbuvir	400 mg	IP
Ribavirin	200 mg	IP

Study Assessments:

On treatment visits will occur at Weeks, 1, 2, 4, 8, 12, 16, 20, and 24/EOT. Following discontinuation or completion of therapy, safety will be assessed through post-treatment Week 4, while efficacy and/or resistance will be assessed through post-treatment Week 24.

Statistical Considerations:

Sample Size:

This is an open-label trial evaluating the combination therapy of DCV+ SOF with RBV for 24 weeks in subjects infected with HCV GT-3 with compensated cirrhosis. The study will include approximately 75 subjects.

For the efficacy analysis, the target sample size of 75 can provide with a 95% confidence that the lower bound of the observed SVR12 rate will exceed 82% with an observed SVR rate of 91%. The primary objective is to determine whether the SVR12 rate, is higher than the historical threshold. The threshold rate is estimated at 79% and is based on the upper bound of the SVR rate from GT3 Cirrhotic subjects in the ALLY 3 study, where SVR12 rate is 63% with a confidence interval of (43.7%, 78.9%).

The lower bound of the two-sided 95% confidence interval (CI) of the SVR12 from this study will be used to compare to the historical threshold (79%). For the primary objective, with 75 subjects it would take a minimum of an observed SVR12 rate of 91% (68/75; 95% CI: 81.7%, 96.2%) for the lower bound of the 95% CI to exceed the threshold, and conclude the SVR12 rate of 24-week DCV/SOF/RBV treatment is higher than the historical threshold

Endpoints:

Primary Endpoint

- Proportion of subjects with SVR12, defined as HCV RNA < LLOQ, target detected (TD) or target not detected (TND) at follow-up Week 12 in all treated subjects.

Key Secondary Endpoint

- The proportion of subjects who achieve SVR12 in the presence and absence of NS5A resistance-associated polymorphisms.

Secondary Endpoint(s)

- On treatment safety, as measured by frequency of deaths, serious adverse events (SAEs), discontinuation due to adverse events (AEs), Grade 3/4 AEs and Grade 3/4 laboratory abnormalities
- The proportion of subjects who achieve HCV RNA < LLOQ, TD or TND at each of the following Weeks: 1, 2, 4, 8, 12, 16, 20, 24, and EOT; post-treatment Week 4 and 24
- The proportion of subjects who achieve HCV RNA < LLOQ, TND at each of the following Weeks: 1, 2, 4, 8, 12, 16, 20, 24, and EOT

Analyses:

Results will be presented for treated subjects. Demographics, baseline characteristics and safety data will also be presented.

Categorical variables will be summarized using counts and percents. Continuous variables will be summarized with univariate statistics (eg, mean, median, standard deviation).

Longitudinal summaries of safety and efficacy endpoints will use pre-defined visit week windows. Windows around planned measurement times will be constructed based on the midpoint between planned study visits. Laboratory measures will be summarized using standard international values and units, and US units will be provided in the appendix.

On-treatment endpoints will be assessed using measurements from the start of study therapy through the last dose of study therapy plus 7 days. Follow-up endpoints will be assessed with measurements after the last dose of study therapy plus 7 days.

Schedule of analyses:

The primary analysis will be performed after all subjects have completed post-treatment Week 12 (SVR12). A final analysis (SVR24) will be performed at study completion. Additional interim efficacy analyses may be performed prior to post-treatment 12 to support external data presentations or correspondences with health authorities.

TABLE OF CONTENTS

TITLE PAGE	1
DOCUMENT HISTORY	2
SYNOPSIS.....	3
TABLE OF CONTENTS.....	7
1 INTRODUCTION AND STUDY RATIONALE	11
1.1 Study Rationale	11
1.1.1 Infection with Genotype 3 HCV	11
1.1.2 Daclatasvir / Sofosbuvir Combination (DCV+SOF)	14
1.1.3 Rationale for Study Design	16
1.1.3.1 Rationale for use of DCV and SOF with RBV in patients infected with GT-3 HCV	16
1.1.3.2 Rationale for Treatment of Cirrhotic Subjects	18
1.1.3.3 Rationale for 24-Week Treatment Duration	20
1.1.3.4 Rationale for use in subjects with HCV/HIV coinfection	20

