8.4.2 Efficacy Analyses

Efficacy endpoints during the on-treatment period will be based on HCV RNA measurements closest to the planned visits within pre-defined visit windows. Efficacy endpoints during the follow-up period will be based on the last HCV RNA measurements in pre-defined visit windows.

The primary analysis for the proportions of patients meeting the efficacy endpoints will be for all treated subjects.

For binary efficacy endpoints including secondary efficacy endpoints, response rates and 2-sided 95% exact Binomial confidence intervals (CIs) will be estimated for each treatment arm.

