8.4.2.1 Primary Efficacy

The primary analysis will be performed after all subjects have completed post-treatment Week 12 (SVR12). A final analysis (SVR24) will be performed at study completion.

The primary analysis for the primary endpoint SVR12 will use all treated subjects, and missing HCV RNA data at follow-up Week 12 will be imputed using the Next Value Carried Backwards (NVCB) approach, ie, missing HCV RNA data in the follow-up Week 12 window will be imputed using the next and closest available HCV RNA measurement after the follow-up Week 12 HCV RNA visit window.

The lower bound of the SVR12 95% confidence interval (CI) will be used to compare to the historical threshold of 79%. If it exceeds 79%, it can be concluded that the primary objective is achieved.

The following sensitivity analyses on the primary endpoint will also be conducted:

- Sensitivity analysis using mITT: SVR12 rates and two-sided 95% CIs will use all treated subjects. The SVR12 status for subjects with missing follow-up Week 12 HCV RNA will be counted as non-responders
- Sensitivity analysis using observed values: SVR12 rates and two-sided 95% CIs will use observed values. The numerator is based on subject meeting the response criteria. However, the denominator is based on treated subjects with HCV RNA at post-treatment Week 12

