7.3.2.2 Baseline Disease Characteristics and Prognostic Factors

All subjects in this study are GT-3 Infected with cirrhosis.

Otherwise, refer to Core SAP Section 7.3.2.2.

7.3.2.3 *Other Baseline Characteristics*

Refer to Core SAP Section 7.3.2.3.

7.4 *Extent of Exposure*

Study therapy of this study is DCV+SOF+RBV.

Refer to Core SAP Section 7.4. In addition, proportions of subjects with RBV dose reduction, and RBV discontinuation will be presented separately. RBV discontinuation will be defined as last RBV dosing date < last treatment dosing date -1. Time to the first RBV dose reduction and time to RBV discontinuation will also be summarized.

Subjects with full RBV dosing, dose reduction or interruptions > 14 days are summarized. A subject listing is generated for all subjects who received a full RBV dose or experienced a reduction or interruption in RBV dose. This listing will include time on study therapy, treatment start and stop dates, weight, target daily dose, total daily dose received, reason for modification, duration adherence, and dose adherence.

7.5 *Efficacy*

For binary efficacy endpoints, 2-sided 95% CIs will be calculated based on exact binomial distribution.

7.5.1 *Primary Efficacy Endpoint*

The primary analysis will be performed after all subjects have reached post-treatment Week 12 (SVR12). A final analysis (SVR24) will be performed at study completion.

The primary analysis for the primary endpoint SVR12 will be computed on all treated subjects, and missing HCV RNA data at follow-up Week 12 will be imputed using the Next Value Carried Backwards (NVCB) approach, ie, missing HCV RNA data in the follow-up Week 12 window

will be imputed using the next and closest available HCV RNA measurement after the follow-up Week 12 HCV RNA visit window.

The lower bound of the SVR12 95% confidence interval (CI) will be used to compare to the historical threshold of 79%. If it exceeds 79%, it can be concluded that the primary objective is achieved.

The following sensitivity analyses on the primary endpoint will also be conducted:

- Sensitivity analysis using mITT (Missing=Non-Responder): SVR12 rates and two-sided 95% CIs will use all treated subjects. The SVR12 status for subjects with missing follow-up Week 12 HCV RNA will be counted as non-responders.

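### The Synopsis gives 68/75 as the minimum result for success; under the plan's own exact 95% interval it is 67/75, and the claimed lower bound above 82% conflicts with the 81.7% printed beside it

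*Protocol*

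**What the plan says.** The sample size text under Statistical Considerations in the Synopsis makes three linked statements.

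- The threshold: "The threshold rate is estimated at 79% and is based on the upper bound of the SVR rate from GT3 Cirrhotic subjects" of an earlier study, for which it reports that the "SVR12 rate is 63% with a confidence interval of (43.7%, 78.9"%).
- The precision at 75 subjects: the lower bound "will exceed 82% with an observed SVR rate of 91"%.
- The bar for success: "with 75 subjects it would take a minimum of an observed SVR12 rate of 91% (68/75; 95% CI: 81.7%, 96.2"%) for the lower bound to exceed the threshold.

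The planned size is not fixed exactly: "The study will include approximately 75 subjects".

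The analysis sections settle the method and the rule. Protocol 8.4.2 prescribes "2-sided 95% exact Binomial confidence intervals (CIs") for binary efficacy endpoints, and SAP 7.5 agrees: "For binary efficacy endpoints, 2-sided 95% CIs will be calculated based on exact binomial distribution". Protocol 8.4.2.1 then compares the lower bound with the threshold: "If it exceeds 79%, it can be concluded that the primary objective is achieved". SAP 7.5.1 states the same rule. Neither section gives a responder count. SAP Table 5.1-1 lists exact intervals for six results at n = 75 and goes from 64 responders straight to 68.

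**The concern.** The lower bound printed for 68/75 is 81.7%, which is 2.7 percentage points above the 79% threshold. At this sample size one responder moves the exact lower bound by about 1.6 points, so a result that clears the threshold by 2.7 points is unlikely to be the smallest that clears it. Separately, a lower bound of 81.7% does not exceed 82%.

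The Synopsis sentence is the only place in the visible text that turns the primary success criterion into a responder count. If it is wrong, the plan gives two answers for one possible result: 67/75 meets the rule in Protocol 8.4.2.1 but misses the Synopsis minimum. The trial is open-label and single-arm, and sites can see HCV RNA, so it is better to settle which statement applies before results are known.

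**Working it through.** **Inputs.** n = 75 and threshold 79% (Synopsis); unrounded source of the threshold 78.9% (Synopsis); two-sided 95% exact binomial interval (Protocol 8.4.2, SAP 7.5); success if the lower bound exceeds 79% (Protocol 8.4.2.1, SAP 7.5.1).

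**Formula.** For x responders out of n, the Clopper-Pearson limits are

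- lower = 2.5% quantile of Beta(x, n − x + 1)
- upper = 97.5% quantile of Beta(x + 1, n − x)

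**Step 1: reproduce the plan's own figures.** For 68/75 the formula gives 81.71% to 96.16%, matching the printed 81.7% and 96.2%. The other five rows of SAP Table 5.1-1 also reproduce. The interval method is therefore not in doubt.

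**Step 2: find the smallest passing count at n = 75.**

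| Responders | Observed | Exact 95% CI | Lower bound above 79%? |
|---|---|---|---|
| 66 | 88.0% | 78.44% to 94.36% | No |
| 67 | 89.3% | 80.06% to 95.28% | Yes |
| 68 | 90.7% | 81.71% to 96.16% | Yes |
| 69 | 92.0% | 83.40% to 97.01% | Yes |

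The minimum is 67.

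**Step 3: look for a reading that gives 68.**

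- Threshold 78.9% instead of 79%: the minimum is still 67 (66 gives 78.44%).
- Wilson interval: 67 (lower bound 80.34%; 66 gives 78.74%).
- Agresti-Coull interval: 67 (80.10%; 66 gives 78.52%).
- Wald interval: 66 (80.65%; 65 gives 78.97%).
- Jeffreys interval: 66 (79.25%; 65 gives 77.64%).

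None of these gives 68.

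**Step 4: the 82% statement.** At 68/75, which the Synopsis itself labels 91%, the lower bound is 81.71%, or 0.3 points below 82%. The first count to exceed 82% is 69/75 (83.40%).

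**Step 5: error rate of each cut-off.** With X ~ Binomial(75, 0.79), P(X ≥ 67) = 0.0149 and P(X ≥ 68) = 0.0060. Both are below the one-sided 2.5% that the interval implies, so stating 67 does not loosen the plan.

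**Step 6: how often the discrepancy could matter.** The visible text states no true SVR12 rate, so the rates below are assumptions.

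| Assumed true rate | P(exactly 67 of 75) |
|---|---|
| 85% | 8.1% |
| 89% | 14.7% |
| 91% | 13.1% |
| 93% | 7.5% |
| 95% | 2.1% |

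At an assumed 91%, the probability of success is 76.9% with the actual cut-off of 67 and 63.8% if 68 were required. The difference, 13.1 points, is the chance of exactly 67.

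**Step 7: other sample sizes.** Because enrolment is approximate, the minimum depends on the number treated: 64/72 (lower bound 79.28%), 66/74 (79.80%), 68/76 (80.31%) and 71/80 (79.72%).

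**The case against.** The best defence is that nothing operative is wrong. The rule is correct in Protocol 8.4.2.1 and SAP 7.5.1, and the Synopsis itself states it in the sentence just before the wrong count, so a careful reader given 67/75 and its interval could reach the right conclusion. The error is also conservative, since it cannot turn a failure into a claimed success. It would show only if exactly 67 of exactly 75 treated subjects responded. All of this stands. It limits the consequence, but it does not make 68 the minimum.

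On the 82% statement, one could say that the sentence refers to a rate of 91% and not to 68/75. Putting 0.91 × 75 = 68.25 responders into the same formula gives a lower bound of 82.13%, which does exceed 82%. But 68.25 responders cannot be observed, no whole count out of 75 equals 91% exactly, and the Synopsis equates 91% with 68/75. Simple rounding of 81.7% to 82% is another possible origin. On either account this is a small matter with no bearing on the 79% decision.

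The text of Protocol 8.1 is not visible, so whether it repeats or qualifies these figures cannot be judged.

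**Conclusion.** The concern holds. With 75 treated subjects and the planned exact interval, the smallest successful result is 67/75 (89.3%), not 68/75 (90.7%), so the stated bar is one responder too high. The lower bound at 68/75 is 81.7%, not above 82%. The first conclusion rests only on n = 75, the two-sided exact 95% interval and the 79% threshold, all taken from the documents, and it is unchanged at 78.9%. The error lies in the description of the bar and not in the test. It should be corrected because it concerns the primary success criterion and one plausible result would be described in two incompatible ways. The probabilities attached to that result depend on assumed true rates.

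**What to change.** In the Synopsis, replace the minimum with wording such as: with 75 treated subjects the minimum is 67/75 (89.3%; exact 95% CI 80.1%, 95.3%); if the number treated differs, the rule that the lower bound exceeds 79% governs (for example 64/72, 66/74, 68/76 or 71/80). Replace the claim about exceeding 82% with a statement that the lower bound is 81.7% for 68/75.

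Make the same corrections in Protocol 8.1 if it repeats these figures. Adding a 67/75 row to SAP Table 5.1-1 would help but is optional, since its printed rows are correct. If a probability of success is ever quoted, label the true rate behind it as an assumption.

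The cost is two sentences in the Synopsis, and the same in 8.1 if needed. Sample size, interval method, decision rule and conduct do not change.

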1.2 Research Hypothesis

Combination therapy with DCV and SOF plus RBV for 24 weeks is safe and demonstrates an SVR12 rate greater than the threshold SVR rate in chronically infected subjects with HCV GT-3 and cirrhosis.

1.3 Objectives(s)

1.3.1 Primary Objective

To demonstrate the SVR12 rate, defined as HCV RNA < LLOQ target detected (TD) or target not detected (TND) as follow-up Week 12 in subjects treated with 24 weeks of DCV+SOF+RBV therapy is greater than the historical threshold SVR rate.

1.3.2 Key Secondary Objective

- To assess the relationship between efficacy and NS5A resistance-associated polymorphisms.

1.3.3 Secondary Objectives

- To assess safety, as measured by the frequency of deaths, serious adverse events (SAE)s, discontinuation due to adverse events (AE)s, Grade 3/4 AEs and Grade 3/4 laboratory abnormalities
- To assess antiviral activity, as measured by:
 - The proportion of subjects who achieve HCV RNA < LLOQ, TD or TND at each of the following Weeks: 1, 2, 4, 8, 12, 16, 20, 24, and EOT; post-treatment Week 4 and 24
 - The proportion of subjects who achieve HCV RNA < LLOQ, TND at each of the following Weeks: 1, 2, 4, 8, 12, 16, 20, 24, and EOT

1.3.4 Exploratory Objectives

1.4 Product Development Background

2 ETHICAL CONSIDERATIONS

2.1 Good Clinical Practice

This study will be conducted in accordance with Good Clinical Practice (GCP), as defined by the International Conference on Harmonisation (ICH) and in accordance with the ethical principles underlying European Union Directive 2001/20/EC and the United States Code of Federal Regulations, Title 21, Part 50 (21CFR50).

The study will be conducted in compliance with the protocol. The protocol and any amendments and the subject informed consent will receive Institutional Review Board/Independent Ethics Committee (IRB/IEC) approval/favorable opinion prior to initiation of the study.

All potential serious breaches must be reported to BMS immediately. A serious breach is a breach of the conditions and principles of GCP in connection with the study or the protocol, which is likely to affect, to a significant degree, the safety or physical or mental integrity of the subjects of the study or the scientific value of the study.

Personnel involved in conducting this study will be qualified by education, training, and experience to perform their respective tasks.

This study will not use the services of study personnel where sanctions have been invoked or where there has been scientific misconduct or fraud (eg, loss of medical licensure, debarment).

2.2 Institutional Review Board/Independent Ethics Committee

Before study initiation, the investigator must have written and dated approval/favorable opinion from the IRB/IEC for the protocol, consent form, subject recruitment materials (eg, advertisements), and any other written information to be provided to subjects. The investigator or BMS should also provide the IRB/IEC with a copy of the Investigator Brochure or product labeling information to be provided to subjects and any updates.

The investigator or BMS should provide the IRB/IEC with reports, updates and other information (eg, expedited safety reports, amendments, and administrative letters) according to regulatory requirements or institution procedures.

2.3 Informed Consent

Investigators must ensure that subjects are clearly and fully informed about the purpose, potential risks, and other critical issues regarding clinical studies in which they volunteer to participate.

In situations where consent cannot be given to subjects, their legally acceptable representatives (as per country guidelines) are clearly and fully informed about the purpose, potential risks, and other critical issues regarding clinical studies in which the subject volunteers to participate.

BMS will provide the investigator with an appropriate (ie, Global or Local) sample informed consent form which will include all elements required by ICH, GCP and applicable regulatory

requirements. The sample informed consent form will adhere to the ethical principles that have their origin in the Declaration of Helsinki.

Investigators must:

- Provide a copy of the consent form and written information about the study in the language in which the subject is most proficient prior to clinical study participation. The language must be non-technical and easily understood.
- Allow time necessary for subject or subject's legally acceptable representative to inquire about the details of the study.
- Obtain an informed consent signed and personally dated by the subject or the subject's legally acceptable representative and by the person who conducted the informed consent discussion.
- Obtain the IRB/IEC's written approval/favorable opinion of the written informed consent form and any other information to be provided to the subjects, prior to the beginning of the study, and after any revisions are completed for new information.

If informed consent is initially given by a subject's legally acceptable representative or legal guardian, and the subject subsequently becomes capable of making and communicating his or her informed consent during the study, consent must additionally be obtained from the subject.

Revise the informed consent whenever important new information becomes available that is relevant to the subject's consent. The investigator, or a person designated by the investigator, should fully inform the subject or the subject's legally acceptable representative or legal guardian, of all pertinent aspects of the study and of any new information relevant to the subject's willingness to continue participation in the study. This communication should be documented.

The confidentiality of records that could identify subjects must be protected, respecting the privacy and confidentiality rules applicable to regulatory requirements, the subjects' signed ICF and, in the US, the subjects' signed HIPAA Authorization.

The consent form must also include a statement that BMS and regulatory authorities have direct access to subject records.

The rights, safety, and well-being of the study subjects are the most important considerations and should prevail over interests of science and society.

